A resource navigator will perform the study intervention. While the navigator will not directly provide counselling or mental health supports, they will serve as a liaison to link the PSWs and other long-term care and retirement home support service staff to these supports. The navigators will hold a degree or diploma in social services/work, psychology or a related field and have at least 2 years experience in these sectors..

11. Interventions

11a. Interventions

Each month, participants in the intervention arm will receive a PDF package by email from a research staff member, which will include wellness, burnout and mental health resources (e.g., how to use the free, self-referral Centre for Addiction and Mental Health service [18]; tips on reducing/preventing burnout [21]), SARS-CoV-2 vaccine infographics [22], a wraparound [20] resource package, and IPAC [17] tips/guidance. Participants that indicated they would like a print copy of the resources in the pre-screening survey (Appendix C) will be provided a copy via mail. Participants will also receive two hours (2, 1-hour sessions) of navigation support sessions from the resource navigator (by phone/zoom) per month for six months (Total 12, 1-hour sessions). While the resource navigator will not directly provide counselling or mental health supports, they will serve as a liaison to link the PSWs and other support service staff (where applicable) to these supports. The resource navigators will hold a degree or diploma in social services/work, psychology or a related field and have at least 2 years of experience in these sectors.

Evaluating the impact of resource navigators to support long-term care and retirement home staff during and beyond COVID-19

Principal Investigators: Drs. [name] and [name]

Research ethics protocol

Version Dates: Sept 7th, 2022

Version Number: 2

In the control arm, participants will receive the monthly educational resources only.

Both intervention and control arms will complete a baseline survey, exit survey (at 6 months) and interview if selected to participate

11b. Modifications

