Participants may be inconvenienced by taking part in components of the study (e.g., exit interviews). The COVID-19 pandemic is also a stressful situation to many; therefore, risks will be mitigated by ensuring participants are aware that they have the option to participate and/or not answer any questions they do not wish to answer. Participants will be able to withdraw from the study at any point with no consequences by notifying a study coordinator, investigator or the resource navigator. Participants may have to withdraw due to end of employment or personal concerns. Preliminary sample size estimations have been calculated to account for participant attrition.

11c. Adherence

To facilitate adherence to the intervention, participants in the intervention arm will receive a package that includes educational resources by email and/or mail each month. Resource navigators will directly reach out to participants in the intervention arm (via email/phone) and will provide them with two hours of navigation support sessions (by phone/zoom) per month for six months. Additionally, during the course of the intervention, the resource navigation will also identify processes to enhance adherence for the six-month period through various methods including personalization of sessions (participant's communication and time preference) and providing ambient information pre-session (session reminders, goal of each session).

11d. Concomitant Care

Due to the nature of this study, all participants will be assessed if they are receiving other interventions related to wellness, which can be self-directed or organization directed. This will also enable the identification co-intervention bias, which can impact on the study outcome

12. Outcome Measures

1. Primary Outcome Measures

The primary outcome for this study is the impact of the intervention on staff wellness. This will be measured by determining the impact of resource navigation on the change in wellness between the 6-month time point and baseline for those who received educational resources and resource navigation compared to those who received educational resources alone.

Participant wellness will be assessed using the Personal Wellbeing Score.[31] The Personal Wellbeing Score measure was selected to align with the World Health Organization's 2004

Evaluating the impact of resource navigators to support long-term care and retirement home staff during and beyond COVID-19

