Via participants’ Ontario Health Insurance Plan (OHIP) number, we will link to the ICES provincial administrative database to obtain participants’ vaccine status, and rates of SARS-CoV-2 infection, hospitalization and death, over the study period. [38, 39]. Unique to the exit survey, study participants will be asked about their satisfaction with the intervention. A process evaluation will be conducted to assess quality and delivery of the study intervention. The resource navigator will track the number, duration and focus of the 1:1 sessions per participant at the end of each individual session using a Process Evaluation- Intervention Tracking Form (Appendix Q). Participant experiences, suggestions for improvement and planning for sustainability will be collected via individual interviews with the resource navigator. A sample of

Evaluating the impact of resource navigators to support long-term care and retirement home staff during and beyond COVID-19

Principal Investigators: Drs. [name] and [name]

Research ethics protocol

Version Dates: Sept 7th, 2022

Version Number: 2

control (n=8-10) and intervention (n=8-10) participants will be interviewed. We will purposively sample the group, with an aim to reflect diversity in gender, age, race and other PROGRESS-plus characteristics

13. Participant Timeline

As noted above, the primary and secondary outcomes will be assessed using a multi-measure baseline and exit survey. Baseline surveys will be conducted 0-30 days after randomization and exit surveys will be conducted at 6 months (182 days) after the randomization date.

Process evaluation data will be collected throughout the duration of the intervention (from 0 days after randomization until the end of intervention (182 days)).

Post-intervention exit interviews will then be conducted at approximately 6-7 months (182-213 days) after the randomization date. These interviews will include a subsample of 8-10 participants from the intervention arm and 8-10 participants from the control arm of the study. See Figure 1 for flow of participants. Note: this will be a rolling recruitment.

Evaluating the impact of resource navigators to support long-term care and retirement home staff during and beyond COVID-19

[figure not shown]
Principal Investigators: Drs. [name] and [name]

Research ethics protocol

Version Dates: Sept 7th, 2022

Version Number: 2

Figure 1. Flow of Participants

14. Sample Size

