This study estimates that the standard deviation (SD) across mean Personal Wellbeing Scores is 10.2.[31] Assuming we will use a t-test to compare the scores across the intervention groups, a medium effect size of 0.5, a SD estimate of 10.2, a false positive error rate of 5% and a power of 80%, the estimated sample size is 64 participants per arm or 128 for the two arms. Including a buffer for participation attrition of 20%, the study will require a total of 154 participants (77 per arm).

Evaluating the impact of resource navigators to support long-term care and retirement home staff during and beyond COVID-19

Principal Investigators: Drs. [name] and [name]

Research ethics protocol

Version Dates: Sept 7th, 2022

Version Number: 2

15. Recruitment

The study team will be using multiple recruitment strategies: circle of contacts, snowball, and advertisements (Appendix A, B, Y). The study team will also leverage partnerships with OPSWA, Ontario LTC Association (OLTCA), Family Councils Ontario (FCO), and other Long Term Care and retirement organizations to recruit PSWs and other service support staff working in Ontario long-term care and retirement homes. All interested potential participants will be provided with a pre-screening survey to determine eligibility, the study information sheet and a consent form..

Methods: Assignment of Interventions (for controlled trials)

16. Allocation

16a. Sequence Generation

Participants will be randomly assigned to either control or intervention group with a 1:1 allocation sequence using computer software and will use block randomization with randomly selected block sizes to keep the enrollment sizes in each arm similar throughout the trial. [40] This will be done under the supervision of the study statistician (BP).

16b. Concealment Mechanism

The study team will use a secure web application called Research Electronic Data Capture (REDCap) to randomly allocate participants to the intervention and control arms, which will conceal the sequence and allocation until the point of assignment. [40]

16c. Implementation

All participants who provide consent for participation and who fulfil the inclusion criteria will be randomized. A statistician from the study team will generate the random allocation sequence. Research coordinators of the study will enroll participants and assign them to a study arm (control or intervention arm).

17. Blinding

17a. Blinding (Masking)

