Due to the nature of the intervention, neither participants nor researchers will be blinded to the study arm; however, statisticians conducting the outcome analysis will be blinded to which arm participants were assigned. PSWs and other support service staff in the same long-term care and retirement home may be randomized to different study arms, which may cause contamination; however, this is unlikely since those in the control arm will not have access to the navigators.

Evaluating the impact of resource navigators to support long-term care and retirement home staff during and beyond COVID-19

Principal Investigators: Drs. [name] and [name]

Research ethics protocol

Version Dates: Sept 7th, 2022

Version Number: 2

17b. Emergency Unblinding

Since direct study participants and researchers will not be blinded throughout the duration of the study, unblinding procedures will not be required or necessary for the purposes of this trial

Methods: Data collection, management, and analysis

18. Data Collection Methods

18a. Data Collection Methods

Data will be collected by the Knowledge Translation Program, Li Ka Shing Knowledge Institute, Unity Health Toronto (KTP-UHT). Baseline and exit surveys will be administered online via REDCap.

The study will use the Dillman Total Design Method (follow up at 1, 3, 7, 10 weeks) to increase survey responsiveness. [40] Participants who indicate interest and meet study criteria will be asked to complete a baseline survey at the beginning of the study (0 weeks). If they do not respond immediately, they will receive reminder emails at 1, 3, 7 and 10 weeks. At the 6-month mark, after study completion (26 weeks), participants will be asked to complete an exit survey. If they do not respond immediately, they will also receive reminder emails at 1, 3, 7 and 10 weeks. However, based on whether there are delays in the ability to recruit participants due to a lack of response to recruitment emails and reminders, there is a possibility that the surveys will not take place at the exact times noted above. If this occurs, we will make sure to note this in our limitations. All survey questions have been reviewed by the steering committee for acceptability, clarity of language and feasibility of format (e.g., mobile friendly access).

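### The baseline survey is scheduled 0–30 days after open-label randomisation, so the change-from-baseline primary outcome may rest on a baseline taken after the arm is known and navigation has begun

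*Combined protocol and SAP*

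**What the plan says.** Section 13 (Participant Timeline) fixes both surveys relative to randomisation: "Baseline surveys will be conducted 0-30 days after randomization and exit surveys will be conducted at 6 months (182 days) after the randomization date". The same section has process-evaluation data collected throughout the intervention, "from 0 days after randomization until the end of intervention (182 days" in all, and adds "Note: this will be a rolling recruitment".

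Four other provisions bear on what this baseline measures:

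- **Section 16c, trigger for randomisation:** "All participants who provide consent for participation and who fulfil the inclusion criteria will be randomized". A completed baseline survey is not a condition.
- **Section 17a, blinding:** "neither participants nor researchers will be blinded to the study arm".
- **Section 12, primary outcome:** "the change in wellness between the 6-month time point and baseline", compared between arms on the Personal Wellbeing Score.
- **Section 11a, intervention:** "two hours (2, 1-hour sessions) of navigation support sessions from the resource navigator (by phone/zoom) per month for six months", 12 sessions in total.

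Other text points to an earlier baseline. Section 18a says that interested people who meet the criteria "will be asked to complete a baseline survey at the beginning of the study (0 weeks"), and Table 1 gives month 0. Section 26a sends the baseline link after consent and names no assignment step in between. A later bullet in Section 26a mentions assignment before the survey invitation, but it lists what consent covers and is weak evidence of order. The Timeline table puts assignment and baseline in one period and the intervention in later ones.

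**The concern.** A baseline for a change score should be measured before anything that differs between arms. Followed as written, Section 13 allows it to be measured afterwards. Three things could go wrong.

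- **Early benefit.** Any navigator benefit already present when the survey is answered is subtracted from the change, so the contrast shrinks.
- **Reaction to allocation.** Learning the arm may alter self-reported wellbeing at baseline, and this can move the contrast either way.
- **Missing baselines.** A participant who is randomised but never returns a baseline has no change score. Once the arm is known, this loss could differ between arms.

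The sections also do not fit together on timing. Section 18a sends baseline reminders at 1, 3, 7 and 10 weeks, counted from the baseline request. If that request is made at randomisation, the last two fall on days 49 and 70, outside the 30-day window.

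**Working it through.** **Inputs from the documents.** SD 10.2, effect size 0.5, 5% error rate, 80% power, 64 per arm, 154 in total with a 20% attrition buffer (Section 14); window 0–30 days and exit at day 182 (Section 13); 12 sessions (Section 11a).

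**Assumed, with no source in the documents.** Linear build-up of the effect; baseline-to-exit correlation r (0.5, range 0.3 to 0.7); a reaction to allocation of 1 or 2 points; 10% or 20% missing baselines. All power figures are from the noncentral t distribution, two-sided 5%.

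**Plan's own figure.** Effect = 0.5 × 10.2 = 5.1 points. A two-sided t-test needs 63.8, rounded up to 64 per arm. This matches Section 14, and power at 64 is 80.1%.

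**Exposure before a late baseline.** Pro rata sessions by day 30 = 12 × 30/182 = 1.98. Share of follow-up elapsed = 30/182 = 16.5%.

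**1. Early benefit.** Contrast remaining = 5.1 × (1 − t/182). SD of change = 10.2 × √(2(1 − r)). With 64 per arm:

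| Baseline day t | Contrast | r = 0.3 (SD 12.07) | r = 0.5 (SD 10.20) | r = 0.7 (SD 7.90) |
|---|---|---|---|---|
| 0 | 5.10 | 66.0% | 80.1% | 95.2% |
| 7 | 4.90 | 62.6% | 77.0% | 93.6% |
| 15 | 4.68 | 58.6% | 73.1% | 91.4% |
| 30 | 4.26 | 50.9% | 65.0% | 85.7% |

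Each row puts every participant on that day. An even spread over days 0–30 has mean day 15, so its power is close to the day-15 row. A t-test on 6-month scores alone (SD 10.2) stays at 80.1%.

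**2. Reaction to allocation, no true effect.** Let the reaction be b points at a post-randomisation baseline, with fraction p left at month 6. The change contrast under the current timing is (p − 1)b. With a pre-randomisation baseline it is pb. SD of change is 10.2 (r = 0.5), 64 per arm. Rejection rates, nominal 5%:

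| p | Current, b = 1 | Current, b = 2 | Pre-randomisation, b = 1 | Pre-randomisation, b = 2 |
|---|---|---|---|---|
| 0 | 8.5% | 19.6% | 5.0% | 5.0% |
| 0.5 | 5.9% | 8.5% | 5.9% | 8.5% |
| 1 | 5.0% | 5.0% | 8.5% | 19.6% |

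**3. Missing baselines (r = 0.5, losses independent).** If exit loss uses the whole buffer, 154 × 0.8 / 2 = 61.6, so 61 per arm and 78.2% power. With 10% of baselines also missing, 61.6 × 0.9 = 55.4, so 55 per arm and 73.8%. With 20% missing, 61.6 × 0.8 = 49.3, so 49 per arm and 68.8%.

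**The case against.** The strongest reply is that the baseline may in practice come first. Sections 18a and 26a describe screened, consenting people being sent the survey without mention of an arm, and the Timeline table has the baseline ahead of the intervention. Section 13's day-0-to-182 window strictly describes process-evaluation tracking, and no passage dates the first session or the moment of disclosure. The reminder conflict depends on when the baseline request is sent. Section 18a's warning that surveys may miss their times is tied to recruitment delays, not to late baselines as such. Figure 1 and the baseline emails (Appendices F and G) were not available to check, and nothing is inferred from them.

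This is why the point is worded as what the plan permits. It does not remove the point: Section 13 is the only explicit rule relative to randomisation, no passage requires the survey before assignment, and a calendar table cannot fix the order for each participant under rolling recruitment.

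The objections to the figures also stand in part. Every time course, correlation, reaction and loss rate is assumed. The correlation, which the plan does not state, matters more than the window. The 65% needs everyone to answer on day 30. The missing-baseline figures add to a fully used buffer; if the same people miss both surveys, 61 per arm remain. The fall from 80% to 78% comes from the attrition allowance, not from baseline timing. The $20 gift card per survey should reduce non-return.

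Finally, a pre-randomisation baseline has a drawback. If the reaction to allocation persists to month 6, it no longer cancels in the change score. On that point alone, the move helps only if less than half of the reaction persists.

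**Conclusion.** The concern holds and should be fixed; confidence is medium because the sections disagree on the order. As written, the primary change score may use a baseline that follows allocation and includes early navigation, so it may not measure the change that Section 12 defines.

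Neither the size nor the direction of the bias can be established. If the effect builds linearly and r is 0.5, the power cost is about 7 percentage points for answers spread evenly over the window (80% to 73%) and about 15 if all come on day 30 (80% to 65%). The false-positive rate could reach 8.5% or 19.6% under an assumed 1- or 2-point reaction that has gone by month 6.

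Only the change contrast is exposed. A comparison of 6-month scores alone, which the wording of Sections 14 and 20a would also allow, does not use the baseline. The main reason to act is validity: a baseline submitted before randomisation cannot be influenced by the arm, and its non-return cannot differ by arm.

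**What to change.** - In Sections 13, 16c, 18a and 26a, require the baseline survey to be submitted before REDCap performs randomisation. Individual items stay optional, as Section 20c provides.
- Delete the 0–30-day post-randomisation window and run the 1, 3, 7 and 10-week baseline reminders before randomisation.
- Keep the randomisation date as day 0 for the day-182 exit survey.
- Check that Figure 1, Appendices F and G and the Timeline table show the same order.
- Have the missing-data plan promised in Section 20c cover Personal Wellbeing Score items skipped at baseline, which this change does not prevent.

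**Cost.** Amendment wording and one REDCap rule, with no extra visits. Consenters who do not submit a baseline are not randomised. At an assumed 10% or 20% non-submission, 154/0.9 = 171.1 or 154/0.8 = 192.5, so about 172 or 193 consenters are needed to randomise 154. Slow responders enter up to about 10 weeks later, so recruitment may take longer. A reaction to allocation that lasts to month 6 would remain in the change contrast, and the report should acknowledge this.

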Once a participant is enrolled and randomized into the study, the team will make a concerted effort to ensure participants are followed throughout the study. Since the study has a short intervention period (6 month) that will be adapted to align current work practices, we anticipate that withdrawal will be minimal. To meet our proposed sample size, we included a buffer for participation attrition of 20%, requiring a total of 154 participants (77 per arm). To address retention of participants in completing data measures, the study will provide an incentive to complete the study surveys, all participants will receive a \$20 gift card upon each survey completion. The study will use the Dillman Total Design Method (follow up at 1, 3, 7, 10 weeks) to increase survey responsiveness.

19. Data Management

Participant data will be de-identified using a participant I.D. and stored on St Michael's Hospital-Unity Health Toronto's secure server. Identifiers and unique study IDs will be recorded on a master linking log. All study information will be stored according to the process described above until 7 years after the end of the study, after which it will be securely destroyed. Only the study team will have access to the identifying personal information collected for this study.

Baseline and exit surveys will be submitted electronically via REDCap. The survey results will be stored on REDCap until downloaded onto our secure encrypted servers at St. Michael's Hospital- Unity Health Toronto for analysis. We will analyze the quantitative responses using descriptive statistics, and the qualitative data using content analysis.

Evaluating the impact of resource navigators to support long-term care and retirement home staff during and beyond COVID-19

Principal Investigators: Drs. [name] and [name]

Research ethics protocol

Version Dates: Sept 7th, 2022

Version Number: 2

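### The target of 154 does not protect 128 evaluable participants against 20% attrition; it covers about 17%, and 20% would need 160

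*Combined protocol and SAP*

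**What the plan says.** Section 14 (Sample Size) gives its inputs as follows.

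- Test: "Assuming we will use a t-test to compare the scores across the intervention groups".
- Effect and spread: "a medium effect size of 0.5, a SD estimate of 10.2".
- Error rates: "a false positive error rate of 5% and a power of 80"%. It does not say whether the 5% is one-sided or two-sided.
- Result before drop-out: "the estimated sample size is 64 participants per arm or 128 for the two arms".
- Result after drop-out: "Including a buffer for participation attrition of 20%, the study will require a total of 154 participants (77 per arm").

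Section 18b (Retention) repeats the step and gives its purpose: "To meet our proposed sample size, we included a buffer for participation attrition of 20%, requiring a total of 154 participants (77 per arm"). Section 11b (Modifications) says, without a percentage: "Preliminary sample size estimations have been calculated to account for participant attrition". The registration data set and Table 1 carry the same 154 (77 per arm). The inflation formula is not shown anywhere.

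**The concern.** An attrition rate is a proportion of the people randomised. To finish with 128 after a fraction *a* is lost, the number randomised must be 128 / (1 − *a*). Multiplying 128 by (1 + *a*) gives a smaller number, and applying the loss to that number leaves fewer than 128. The stated 154 matches the multiplication and not the division.

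What is at stake is the meaning of the target. A reader of Sections 14 and 18b will take 154 as a number that still delivers 80% power if a fifth of participants are lost. If it does not, the sample-size statement is inaccurate and would be carried into the trial report.

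**Working it through.** **Inputs, all from Section 14:** effect size d = 0.5, SD 10.2 (a difference of 0.5 × 10.2 = 5.1 points), 5% error rate, 80% power, 128 participants before drop-out, 20% attrition, 154 after drop-out. Allocation is 1:1 (Section 16a).

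**1. Base size.** For a two-sample t-test (noncentral t), the number per arm for 80% power at d = 0.5 is:

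- two-sided 5%: 63.77, rounded up to 64, which is the plan's figure;
- one-sided 5%: 50.15, rounded up to 51, which is not.

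The plan's 64 is therefore reproduced, and a two-sided test is inferred from it.

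**2. How 154 arises.**

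- Multiplying: 128 × 1.2 = 153.6, so 154; per arm 64 × 1.2 = 76.8, so 77. Both stated figures are matched.
- Dividing: 128 / 0.8 = 160; per arm 64 / 0.8 = 80. Neither matches.

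The shortfall is 160 − 154 = 6 participants (3 per arm), too large to be rounding.

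**3. What 154 covers.**

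- Largest attrition that leaves 128: 1 − 128/154 = 16.9%, that is 77 − 64 = 13 per arm.
- Remaining after 20% attrition: 154 × 0.8 = 123.2, or 61.6 per arm, below 128.

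**4. Power for d = 0.5, two-sided 5%, by number lost per arm from 77.**

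| Lost per arm | Attrition | Evaluable per arm | Power |
|---|---|---|---|
| 0 | 0% | 77 | 86.9% |
| 13 | 16.9% | 64 | 80.1% |
| 14 | 18.2% | 63 | 79.5% |
| 15 | 19.5% | 62 | 78.9% |
| 15.4 | 20.0% | 61.6 | 78.6% |
| 16 | 20.8% | 61 | 78.2% |

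At exactly 20% attrition the loss is 80.1 − 78.6 = 1.5 points. In whole participants, 123 split 62/61 gives 78.5%. The effect detectable with 80% power at 61.6 per arm is 0.509 SD instead of 0.50.

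**The case against.** The best defence is that a 20% buffer can mean 20% added on top. Read that way, the sentence describes 154 and 77 exactly. No section predicts that 20% will be lost, and Section 18b expects minimal withdrawal. Section 11b names no percentage and fits either reading. Since the formula is not shown, multiplication by 1.2 is an inference.

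Some of this stands. Section 11b does not settle the matter, and the formula is indeed inferred, although it is the one that yields both stated figures. The add-on reading does not rescue the statement, however. Sections 14 and 18b both attach the 20% to participant attrition, and Section 18b says the buffer exists so that the proposed sample size is met. At 20% attrition it is not met. If an add-on was intended, the text still needs to say what loss it tolerates.

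A second objection is that the effect is negligible beside the uncertainty in a generic medium effect size and an SD from one cited source. That is a fair reason for a low rating, but it does not make the figure right.

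A third is that any restated limit depends on equal loss in the two arms, and that attrition is not the only way to lose data. Both points are true. With 26 lost in all but unequally, power is 79.7% for a 71/57 split and 79.2% for 74/54, so imbalance costs less than one point. In addition, the primary outcome is a change from baseline (Section 12), all survey questions are optional and the missing-data plan is still to be developed (Section 20c), and participants may have their data removed until the analysis stage (Section 22). In this calculation attrition should therefore be read as any loss of an evaluable primary outcome.

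**Conclusion.** The concern holds and is minor. As written, 154 is presented as allowing for 20% attrition, but it preserves the plan's 128 evaluable participants only up to about 17%. At 20% the number falls to about 123 and power to about 78.6%. The trial is not materially underpowered by this: the gap is six participants, it matters only if more than 13 per arm are lost, and with full retention power would be 86.9%.

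The power figures assume a two-sided 5% t-test (inferred from the 64 per arm), a standardised effect of 0.5 on whichever score the test compares, and equal loss in the two arms. The comparison of 154 with 160 needs none of these; it rests only on the plan's 128 and its 20%.

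**What to change.** Keep the target of 154 and correct the wording.

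- **Section 14**, replacing the sentence on the buffer: *We will randomise 154 participants (77 per arm). This keeps 64 per arm evaluable, and so 80% power, for attrition up to about 17% (13 per arm). At 20% attrition (about 123 evaluable) power is about 78.6% under the same assumptions (two-sided 5% t-test, effect size 0.5).*
- **Section 18b:** describe the allowance as attrition of about 17% in place of the 20% buffer.
- **Section 14:** state that the 5% test is two-sided, if that is what was used.

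The cost is two sentences in Section 14 and one phrase in Section 18b. Enrolment, conduct, analysis and the 154 shown elsewhere are unchanged; the stated allowance simply becomes slightly less favourable. If the investigators want true protection against 20% attrition, the target would have to be 160 (80 per arm), with the figures in the registration data set, Table 1, Section 18b and the budget changed to match.
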